### **Accumulation Ratio**

To investigate whether the dose of LT3001 drug product is accumulated in the multiday regimen, the potential dose accumulation effect will be assessed by comparing PK parameters of the first dose and the last dose in the multi-day TID regimen of LT3001 drug product. The comparisons will be conducted for occasions when LT3001 is alone or is coadministered with aspirin, clopidogrel, apixaban, or dabigatran.

For each cohort based on a linear mixed-effects model with Day (Day of first dose and Day of last dose) as a fixed effect, and subject as a random effect on log-transformed data, the geometric means and corresponding 95% CIs for  $AUC_{0-t}$ ,  $AUC_{0-\tau}$ ,  $C_{max}$ , and  $C_{trough}$  will be presented by exponentiating the model-based least-squared means. The geometric mean ratios (last dose/first dose) and the corresponding 90% CIs will also be calculated for each cohort based on this model to assess accumulation.

### **Interaction with Aspirin**

To assess the effect of aspirin on LT3001, a linear mixed-effects model with Day (Day 1 and Day 6) as a fixed effect, and subject as a random effect on log PK-parameters will be used to calculate 90% confidence intervals (CIs) for the geometric mean ratios (GMRs) of  $AUC_{0-t}$ ,  $AUC_{0-\tau}$ ,  $C_{max}$ , and  $C_{trough}$  by exponentiating the Least Square Mean Differences. The criteria of 90% CI within 50-200% of weak-effect boundaries will be used first for assessment. Only when the first criteria are satisfied, the second criteria of 90% CI within 80%-125% of no-effect boundaries will be used for further assessment.

The effect of LT3001 on the PK of aspirin will be assessed by comparing PK parameters of aspirin with and without LT3001 using a linear model similar to above with Day (Day 5 and Day 8) as fixed effect. PK parameters for comparison include  $AUC_{(0-t)}$  and  $C_{max}$ .

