### Drug/Drug Interactions

The effect of aspirin, clopidogrel, apixaban or dabigatran on the PK of LT3001 as well as the effect of LT3001 on the PK of aspirin, clopidogrel, apixaban or dabigatran will be assessed by comparing steady-state PK parameters of LT3001 and these concomitant medications.

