Platelet function test		X i					X j	X k					X l	X	X	
Congulation k	X	X i					X j	X k					X l	X	X	
Hematology test l	X	X i					X						X	X	X	
Clinical chemistry test m	X	X i					X						X	X	X	
Urinalysis n	X	X i					X						X	X	X	
Discharge													X			
Prior and concomitant medication	X								X							
Adverse event									X							

ECG = electrocardiogram; ET = early termination; PK = pharmacokinetic

- a Virology tests will include HIV antibody, HBsAg, hepatitis C virus antibody, and COVID-19 antibody.
- b Demographics will include age, gender, height, body weight, BMI and race. On Day -1, only body weight will be measured.
- c Serum pregnancy test will be performed in female subjects of childbearing potential within 24 hours prior to the first drug treatment on Day 1.
- d The dose of clopidogrel on Day 7, Day 8 and Day 9 will be followed immediately by 0.025 mg/kg LT3001 administered as a 15-minute IV infusion.
- e Physical examination will be performed at screening visit, pre-dose on Day 1, the end of clopidogrel single treatment on Day 6, the end of combination treatment on Day 9 and follow-up visit on Day 16.
- f Vital signs will include body temperature, blood pressure, respiratory rate, and heart rate. Measurements will be made after the subject has rested in a supine position for at least 3 minutes. Blood pressure will be assessed in seated and supine position at pre-dose and 60 minutes after dosing infusion, only supine position at 20 minutes after dosing/infusion. Vital signs will be assessed at screening visit, Day 1 to 6 (pre-dose), Day 7 to Day 9 (each LT3001 dosing period at pre-dose, 20 minutes and 60 minutes after infusion is initiated) and follow-up visit on Day 16.
- g A 12-lead ECG assessment will be performed at screening visit and at pre-dose and 1 hour after taking clopidogrel on Day 2 to Day 6, and after 1 hour after the infusion is initiated of the first dose of LT3001 on Day 7 to Day 9 and follow-up visit on Day 16.
- h PK blood samples of LT3001 will be collected on Day 1, on the first dose of LT3001 on Day 7 and the 3rd dose of Day 9 at pre-dose, 5±1, 10±1, 15±1, 20±1, 25±1, 30±1, 45±1, and 60±5 minutes after infusion is initiated.

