### **Interaction with Clopidogrel**

To assess the effect of clopidogrel on LT3001, a linear mixed-effects model with Day (Day 1 and Day 7) as a fixed effect, and subject as a random effect on log PK-parameters will be used to calculate 90% confidence intervals (CIs) for the geometric mean ratios (GMRs) of  $AUC_{0-t}$ ,  $AUC_{0-\tau}$ ,  $C_{max}$ , and  $C_{trough}$  by exponentiating the Least Square Mean Differences. The criteria of 90% CI within 50-200% of weak-effect boundaries will be used first for assessment. Only when the first criteria are satisfied, the second criteria of 90% CI within 80%-125% of no-effect boundaries will be used for further assessment.

The effect of LT3001 on the PK of clopidogrel will be assessed by comparing PK parameters of clopidogrel with and without LT3001 using a linear model similar to above with Day (Day 6 and Day 9) as fixed effect. PK parameters for comparison include  $AUC_{(0-t)}$  and  $C_{max}$ .

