### **Interaction with Apixaban**

To assess the effect of apixaban on LT3001, a linear mixed-effects model with Day (Day 1 and Day 5) as a fixed effect, and subject as a random effect on log PK-parameters will be used to calculate 90% confidence intervals (CIs) for the geometric mean ratios (GMRs) of  $AUC_{0-t}$ ,  $AUC_{0-\infty}$ ,  $C_{max}$ , and  $C_{trough}$  by exponentiating the Least Square Mean Differences. The criteria of 90% CI within 50-200% of weak-effect boundaries will be used first for assessment. Only when the first criteria are satisfied, the second criteria of 90% CI within 80%-125% of no-effect boundaries will be used for further assessment.

The effect of LT3001 on the PK of apixaban will be assessed by comparing PK parameters of apixaban with and without LT3001 using a linear model similar to above with Day (Day 4 and Day 7) as fixed effect. PK parameters for comparison include  $AUC_{(0-t)}$  and  $C_{max}$ .

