### **Interaction with Dabigatran**

To assess the effect of dabigatran on LT3001, a linear mixed-effects model with Day (Day 1 and Day 5) as a fixed effect, and subject as a random effect on log PK-parameters will be used to calculate 90% confidence intervals (CIs) for the geometric mean ratios (GMRs) of  $AUC_{0-t}$ ,  $AUC_{0-\infty}$ ,  $C_{max}$ , and  $C_{trough}$  by exponentiating the Least Square Mean Differences. The criteria of 90% CI within 50-200% of weak-effect boundaries will be used first for assessment. Only when the first criteria are satisfied, the second criteria of 90% CI within 80%-125% of no-effect boundaries will be used for further assessment.

The effect of LT3001 on the PK of dabigatran will be assessed by comparing PK parameters of dabigatran with and without LT3001 using a linear model similar to above with Day (Day 4 and Day 7) as fixed effect. PK parameters for comparison include  $AUC_{(0-t)}$  and  $C_{max}$ .

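### The formal interaction verdict for LT3001 rests on the first combination infusion; the last-dose profile is read only as accumulation and never compared with LT3001 alone

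*SAP*

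**What the plan says.** **Effect of the partner on LT3001 (SAP 8.3).** Every model has two Day levels: LT3001 alone, and the first combination day.
- Aspirin: "a linear mixed-effects model with Day (Day 1 and Day 6) as a fixed effect".
- Clopidogrel: "a linear mixed-effects model with Day (Day 1 and Day 7) as a fixed effect".
- Apixaban: "To assess the effect of apixaban on LT3001, a linear mixed-effects model with Day (Day 1 and Day 5) as a fixed effect".
- Dabigatran: "To assess the effect of dabigatran on LT3001, a linear mixed-effects model with Day (Day 1 and Day 5) as a fixed effect".

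The 90% CI of this ratio is judged first against 50-200% and then, if that is met, against 80-125%.

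**Last combination dose.** The Cohort 2 schedule in SAP 4.2 (footnote h) samples LT3001 on Day 1, then "on the first dose of LT3001 on Day 7 and the 3 rd dose of Day 9 at pre-dose", with the final sample at 60 minutes. In SAP 8.3 the last-dose profile is used only under Accumulation Ratio: "The geometric mean ratios (last dose/first dose) and the corresponding 90% CIs will also be calculated for each cohort". No boundaries apply to that ratio.

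**Reverse direction.** The models for the effect of LT3001 on the partner do use the last combination day: Day 5 against 8, 6 against 9, 4 against 7 and 4 against 7.

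**Protocol.** The synopsis says that interactions in both directions "will be assessed by comparing steady-state PK parameters of LT3001 and these concomitant medications". Section 10.3.2 defines Day only as with or without the concomitant drug and names no days. SAP section 2 says that the SAP's methods supersede the protocol's.

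**The concern.** The regimen under study is nine combination infusions over three days. The statement that a partner has no effect on LT3001 would come from one of them, and that one falls at a particular moment: the partner dose has only just been swallowed. The ninth infusion comes 6 h after the morning partner dose and after two full days of coadministration. It tests a different condition, yet it never meets the LT3001-alone reference.

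If LT3001 exposure were raised only in that later condition, the interaction ratio would stay near 1 and the last/first ratio would rise under the heading of accumulation. A reader of the report could then draw the wrong conclusion twice: no interaction, and LT3001 accumulates.

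**Working it through.** **1. The plan's own figures.** Fraction of steady state = 1 - 2^(-t/half-life). From the first partner dose (schedule hour 25) to the first combination infusion (hour 97), t = 72 h. At the longest stated half-lives:
- Apixaban: 72/14 = 5.14 half-lives, 97.2% (stated: over 5 half-lives, 97%).
- Dabigatran: 72/17 = 4.24 half-lives, 94.7% (stated: over 4 half-lives, 94%).

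Both reproduce.

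**2. Partner build-up still to come.** The last infusion is at hour 151, so t = 126 h. The fractions are 99.8% and 99.4%. The increases are 99.80/97.17 = 1.027 (apixaban) and 99.41/94.69 = 1.050 (dabigatran). Multi-day build-up of these two drugs is therefore a small part of the problem. No half-life is given for aspirin or clopidogrel.

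**3. Timing within the day.** The schedules put the third-day morning partner dose and LT3001 dose 9 at these hours:

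| Cohort | Partner | LT3001 dose 9 | Gap |
|---|---|---|---|
| 1 | 169 | 175 | 6 h |
| 2 | 193 | 199 | 6 h |
| 3 and 4 | 145 | 151 | 6 h |

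The first combination infusion follows the partner dose immediately. The previous partner dose was 24 h earlier (aspirin, clopidogrel) or 12 h earlier (apixaban, dabigatran). Simple decay over 12 h, 2^(-12/half-life), leaves 40-55% for apixaban (9-14 h) and 50-61% for dabigatran (12-17 h). The documents do not say how much of the new dose is absorbed within the 60-minute sampling window.

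The safety schedule recognises this difference. Platelet function and coagulation on the partner alone are measured at 15 minutes and at 6 h 15 minutes after dosing, which matches the ends of the first and third daily infusions.

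**4. Precision of the missing contrast.** Paired log-scale analysis, n = 12: 90% CI factor = exp[t(0.95, 11 df) x sqrt(2 ln(1 + CV²)/12)]. Within-subject CV is not in the documents and is assumed.

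| CV | Factor | 90% CI around 1.00 |
|---|---|---|
| 15% | 1.116 | 0.896-1.116 |
| 20% | 1.156 | 0.865-1.156 |
| 25% | 1.198 | 0.835-1.198 |
| 30% | 1.240 | 0.806-1.240 |

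**5. What the verdict would show.** With complete data, last/Day 1 = (first/Day 1) x (last/first). For example, 1.00 x 1.30 = 1.30, reported as no interaction and 1.30-fold accumulation. The CI of the product cannot be derived from the two planned CIs.

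Simulation (50,000 cohorts per scenario, n = 12), with true first-dose ratio 1.00 and true last-dose ratio 1.50:

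| CV | Planned CI within 80-125% | Last/Day 1 CI within 80-125% | Last/Day 1 CI wholly above 125% |
|---|---|---|---|
| 15% | 92% | about 0% | 87% |
| 20% | 66% | about 0% | 68% |
| 25% | 36% | about 0% | 52% |
| 30% | 16% | about 0% | 42% |

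The planned column is the same, within simulation error, when the true last-dose ratio is 1.00. With a true last-dose ratio of 2.00, the planned CI meets 50-200% in about 100% of cohorts at these CVs; the last/Day 1 CI does so in about 5%.

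**The case against.** **The planned contrast is the like-for-like one.** Part B has a single LT3001-alone infusion. Comparing it with the first infusion on partner pre-treatment isolates the partner effect. A ninth-dose/single-dose ratio also contains any LT3001 accumulation, so judging it by the same boundaries could turn pure accumulation into an apparent interaction. This stands: the planned test should stay, and the added ratio should not be a pass/fail criterion.

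**Pre-dosing deals with build-up.** Partners are given alone for three to five days first, with loading doses for aspirin and clopidogrel. For apixaban and dabigatran this largely stands (steps 1 and 2). It does not answer the within-day timing, or an effect that needs repeated coadministration.

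**Nothing is lost.** A reader might infer that a late rise would go undetected. The documents do not support that. The last/first ratio is reported for each cohort with a 90% CI, and Part A gives the same ratio without a partner. What is absent is the comparison with LT3001 alone, its CI, and any plan to read Parts A and B together; SAP section 4 has them analysed separately.

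**The synopsis wording.** A reader might also infer that last dose/Day 1 is the steady-state comparison that the synopsis describes. It is not, because Day 1 is a single dose. The synopsis shows only that the protocol and SAP wording need reconciling.

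**The accumulation model.** Its first dose might be read as Day 1. The sentence introducing it restricts it to the multi-day TID regimen, and the ratio would be labelled accumulation either way.

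**Conclusion.** The point holds as a gap in interpretation. In all four cohorts, a no-effect finding for LT3001 applies to the first coadministered infusion, taken mostly around partner trough, and cannot respond to an effect present only at the last infusion. Such an effect would appear in the report, but under accumulation and without boundaries.

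The size is conditional. The 1.30 and 1.50 ratios and the CVs are illustrations, and the documents give no evidence that a late interaction occurs. Nor would the added estimate always be decisive: around 1.30, the 90% CI is 1.30/1.116 to 1.30 x 1.116 = 1.16-1.45 at CV 15%, and 1.30/1.240 to 1.30 x 1.240 = 1.05-1.61 at CV 30%. Both straddle 1.25.

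Last-dose sampling is legible only for Cohort 2. For the others it is inferred from the accumulation model, which needs it. Protocol 9.2 does not anticipate accumulation, which makes a last-dose/Day 1 ratio interpretable as long as Part A agrees.

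**What to change.** In each of the four interaction sections of SAP 8.3:

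1. Keep first combination dose/Day 1 as the interaction test, with the 50-200% and 80-125% boundaries.
2. Fit Day with three levels (Day 1, first combination dose, last combination dose). Report last combination dose/Day 1 for AUC and Cmax with its 90% CI, labelled as a supportive interaction estimate without a pass/fail rule.
3. State which fit supplies the CI for the test in item 1. With complete data and a common residual variance, the three-level fit has 2 x 11 = 22 residual degrees of freedom instead of 11.
4. Show the Part B last/first ratio beside the Part A last/first ratio.
5. State in advance that, if the last-dose ratio is raised and Part A shows no comparable accumulation, a no-effect conclusion is limited to the first coadministered dose and the Part B rise is not called accumulation.
6. Reconcile the synopsis's steady-state wording with the days that the SAP compares.

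The cost is SAP text and one extra contrast per parameter, from profiles that the accumulation model already requires. No new subjects, visits or samples are needed, provided that last-dose sampling in Cohorts 1, 3 and 4 is as inferred. The downside is that the added ratio mixes interaction with any true accumulation, which is why item 4 must accompany it. The Part A dose level is blacked out in the public documents, so the sponsor should confirm that the regimens are comparable.

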### **Interaction with Clopidogrel**

To assess the effect of clopidogrel on LT3001, a linear mixed-effects model with Day (Day 1 and Day 7) as a fixed effect, and subject as a random effect on log PK-parameters will be used to calculate 90% confidence intervals (CIs) for the geometric mean ratios (GMRs) of  $AUC_{0-t}$ ,  $AUC_{0-\tau}$ ,  $C_{max}$ , and  $C_{trough}$  by exponentiating the Least Square Mean Differences. The criteria of 90% CI within 50-200% of weak-effect boundaries will be used first for assessment. Only when the first criteria are satisfied, the second criteria of 90% CI within 80%-125% of no-effect boundaries will be used for further assessment.

The effect of LT3001 on the PK of clopidogrel will be assessed by comparing PK parameters of clopidogrel with and without LT3001 using a linear model similar to above with Day (Day 6 and Day 9) as fixed effect. PK parameters for comparison include  $AUC_{(0-t)}$  and  $C_{max}$ .

### **Interaction with Apixaban**

To assess the effect of apixaban on LT3001, a linear mixed-effects model with Day (Day 1 and Day 5) as a fixed effect, and subject as a random effect on log PK-parameters will be used to calculate 90% confidence intervals (CIs) for the geometric mean ratios (GMRs) of  $AUC_{0-t}$ ,  $AUC_{0-\infty}$ ,  $C_{max}$ , and  $C_{trough}$  by exponentiating the Least Square Mean Differences. The criteria of 90% CI within 50-200% of weak-effect boundaries will be used first for assessment. Only when the first criteria are satisfied, the second criteria of 90% CI within 80%-125% of no-effect boundaries will be used for further assessment.

The effect of LT3001 on the PK of apixaban will be assessed by comparing PK parameters of apixaban with and without LT3001 using a linear model similar to above with Day (Day 4 and Day 7) as fixed effect. PK parameters for comparison include  $AUC_{(0-t)}$  and  $C_{max}$ .

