## **Part B**

Part B is open-label without placebo control. Approximately 48 subjects will be sequentially enrolled into four cohorts with 12 subjects in each cohort.

The first 3 subjects of each cohort will be “sentinel subjects”. After each sentinel subject completes the first day of combination treatments, the Investigator will review all available safety data from the sentinel subjects. If considered safe to do so, each sentinel subject will receive the remaining combination treatments.

The remaining combination treatments in a sentinel subject may not proceed in the event of any of the following:

- A subject experiences any severe hemorrhage which is assessed as related to the combination treatment
- A subject treated with LT3001 drug product experiences any SAE related to study drug (at least possibly related)
- Safety concerns per the Investigator's clinical judgment

The dosing schema is summarized below.

Each Cohort of Part B	Sentinel Subjects	Remaining Subjects
Number of Subjects	3	9

In **Cohort 1**, each subject will receive a single 15-minute infusion of LT3001 [REDACTED] on Day 1. Each subject will receive multiple-dose aspirin as follows: a loading dose of 325 mg aspirin on the morning of Day 2 followed by a daily maintenance dose of 81 mg aspirin on Days 3 through 8. The regimen is intended to achieve its maximal inhibitory effects on platelet function. Aspirin will be administered after breakfast. On the morning of Day 6, the dose of aspirin will be followed by the first dose of LT3001 [REDACTED] administered as a 15-minute IV infusion. Subjects will receive 9 doses of LT3001 on Days 6 through 8 (three doses per day with three hours between doses). Each subject will be admitted into the study site on Day -1, stay until Day 8, and will have a follow-up visit on Day 15.

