In **Cohort 2**, each subject will receive a single 15-minute infusion of LT3001 [REDACTED] on Day 1. Each subject will receive multiple-dose clopidogrel as follows: a loading dose of 300 mg clopidogrel on Day 2 followed by a daily maintenance dose of 75 mg clopidogrel on Days 3 through 9, a dosing paradigm consistent with clinical use in relevant indications. Clopidogrel will be administered after breakfast. On Day 7, the dose of clopidogrel will be followed by the first dose of LT3001 [REDACTED] administered as a 15-minute IV infusion. Subjects will receive 9 doses of LT3001 on Days 7 through 9 (three doses per day with three hours between doses). Each subject will be admitted into the study site on Day -1, stay until Day 10, and will have a follow-up visit on Day 16.

In **Cohort 3**, each subject will receive a single 15-minute infusion of LT3001 [REDACTED] on Day 1. Each subject will receive multiple-dose apixaban as follows: 5 mg apixaban twice daily (BID) every 12 hours (q12h) on Days 2 through 7. The morning doses of apixaban will be given after breakfast. Given that the half-life of apixaban is 9 to 14 hours, the 3-day apixaban BID treatment allows for reaching over 5 half-lives and 97% steady state of apixaban before the coadministration of apixaban and LT3001. On Day 5, the first dose of apixaban will be followed by the first dose of LT3001 [REDACTED] administered as a 15-minute IV infusion. Subjects will receive 9 doses of LT3001 on Days 5 to 7 (three doses per day with three hours between doses). Each subject will be admitted into the study site on Day -1, stay until Day 8, and will have a follow-up visit on Day 14.

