**Table 4 Schedule of Activities for Part B, Cohort 3**

Procedures	Screening Period		Treatment Period														Follow-up	ET s			
	Day -30 to -2	Day -1	Day 1	Day 2	Day 3	Day 4	Day 5			Day 6			Day 7			Day 8	Day 14				
		Hour a	1	25	37	49	61	73	85	97	100	103	109	121	124	127	133	145	148	151	169
Informed consent	X																				
Urine drug/cotinine/alcohol test	X		X t																		
Virology test s	X																				
Demographics b	X		X																		
Medical and surgical history	X																				
Check In			X																		
Serum pregnancy test c			X																		
Apixaban d				X	X	X	X	X	X				X	X			X	X			
LT3001 drug product				X t						X	X	X		X	X	X		X	X	X	
Physical examination e	X			X					X									X		X	X
Vital sign f	X		X	X	X	X		X		X	X	X		X	X	X		X	X	X	
12-lead ECG assessment g	X		X	X	X	X		X		X				X				X		X	X
LT3001PK blood sample																					
Apixaban PK blood sample j																					
Platelet function test			X k						X k	X l								X m		X	X
Coagulation n	X		X t						X k	X l								X m		X	X
Hematology test o	X		X t						X									X		X	X
Clinical chemistry test p	X		X t						X									X		X	X
Urinalysis q	X		X t						X									X		X	X
Discharge																		X			

Prior and concomitant medication	X	X	X
Adverse event	X	X	X

ECG = electrocardiogram; ET = early termination; PK = pharmacokinetic

- a. Virology tests will include HIV antibody, HBsAg, hepatitis C virus antibody, and COVID-19 antibody.
- b. Demographics will include age, gender, height, body weight, BMI and race. On Day -1, only body weight will be measured.
- c. Serum pregnancy test will be performed in female subjects of childbearing potential within 24 hours prior to the first drug treatment on Day 1.
- d. The first dose of apixaban on Day 5, Day 6 and Day 7 will be followed immediately by [REDACTED] LT3001 administered as a 15-minute IV infusion
- e. Physical examination will be performed at screening visit, pre-dose on Day 1, the end of apixaban single treatment on Day 4, the end of combination treatment on Day 7 and follow-up visit on Day 14.

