#### **10.3.2. Pharmacokinetic Analyses**

All PK analyses will be performed on the Pharmacokinetic Analysis Set. The PK parameters will be calculated, as appropriate, using a non-compartmental approach.

Plasma concentrations will be summarized by cohort over each scheduled sampling time using descriptive statistics. Individual plasma concentration data versus actual time points will be presented in listings. Pharmacokinetic parameters will be summarized by dose using descriptive statistics. Individual PK parameters will be presented in a data listing.

The effect of aspirin, clopidogrel, apixaban or dabigatran on the PK of LT3001, as well as the effect of LT3001 on the PK of aspirin, clopidogrel, apixaban or dabigatran, will be assessed by comparing PK parameters of LT3001 and these concomitant medications. A linear mixed-effects model with fixed factors for Cohort and Day (day of with/without concomitant drug use), and subject as random effect on log PK-parameter will be used to calculate 90% confidence intervals for the geometric mean ratio of the  $AUC_{0-t}$ ,  $AUC_{0-\infty}$ ,  $AUC_{0-\tau}$  and  $C_{max}$ . Differences between treatments when LT3001 drug product was administered alone or with aspirin, clopidogrel, apixaban or dabigatran will be calculated for LT3001, aspirin, clopidogrel, apixaban, and dabigatran using ratios of geometric least squares mean and 90% confidence intervals (CI). The criteria of 90% CI within 50-200% of weak-effect boundaries will be firstly used for assessment. Only when the first criteria are satisfied, the second criteria of 90% CI within 80-125% of no-effect boundaries will be used for further assessment.

To investigate whether the dose of LT3001 drug product is accumulated in the 3-day TID regimen, the potential dose accumulation effect will be assessed by comparing PK parameters of the first dose and

the last dose in the multi-day TID regimen of LT3001 drug product. The comparisons will be conducted for occasions when LT3001 is alone or is coadministered with aspirin, clopidogrel, apixaban, or dabigatran. PK parameters for comparison include  $AUC_{0-t}$  and  $C_{max}$ .

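### SAP 8.3 compares partner-drug exposure on AUC(0-t) and Cmax without the fixed-interval AUC0-τ, so the Cohort 3 and 4 ratios depend on Day 7 dosing and sampling that the documents leave unsettled

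*SAP*

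**What the plan says.** Protocol 10.3.2 fits a mixed model that "will be used to calculate 90% confidence intervals for the geometric mean ratio of the" AUC0-t, AUC0-∞, AUC0-τ and Cmax. It covers both directions of interaction: the differences "will be calculated for LT3001, aspirin, clopidogrel, apixaban, and dabigatran using ratios of geometric least squares mean and 90% confidence intervals". The 50–200% and then 80–125% criteria follow. The synopsis says the effects "will be assessed by comparing steady-state PK parameters of LT3001 and these concomitant medications".

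SAP 8.3 is narrower for the partner drugs. In Cohort 3, "The effect of LT3001 on the PK of apixaban will be assessed by comparing PK parameters of apixaban with and without LT3001", with Day 4 against Day 7 and two parameters, AUC(0-t) and Cmax. The other three paragraphs match: dabigatran Day 4 against Day 7, aspirin Day 5 against Day 8, clopidogrel Day 6 against Day 9. AUC0-τ is in the Part B list of derived parameters for the partner drugs. AUC0-t is defined there as ending at the last quantifiable concentration. SAP section 2 says that SAP methods amend or supersede those of the protocol.

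On dosing, the Cohort 3 text gives "5 mg apixaban twice daily (BID) every 12 hours (q12h) on Days 2 through 7", and Cohort 4 has the same pattern. In "Table 4 Schedule of Activities for Part B, Cohort 3" the Day 5 and Day 6 columns include evening hours 109 and 133. Day 7 has hours 145, 148 and 151, and the next column is hour 169. There is no hour 157. The Cohort 4 schedules in both documents also lack it.

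**The concern.** A day-to-day AUC ratio measures an interaction only if the two areas cover the same length of time and the same doses. AUC0-τ fixes this by definition. AUC(0-t) does not: its end point comes from the data, and the SAP sets no common cut-off for the two days.

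For once-daily drugs the exposure to this weakness is limited to sampling length. For the twice-daily drugs, a profile that runs past 12 h may contain one dose or two. The dosing text and the schedule columns disagree on whether a second dose is given on Day 7, which is the combination day in the model. If the Day 4 area held two doses and the Day 7 area one, the shortfall would be reported as LT3001 lowering anticoagulant exposure.

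**Working it through.** **Inputs.** Half-lives from Protocol 5.1: apixaban 9–14 h, dabigatran 12–17 h. First partner dose at hour 25, then every 12 h; Day 4 starts at hour 73 and Day 7 at hour 145. There are 12 subjects per cohort. Assumed, because the documents do not give them: one-compartment kinetics; bolus input, or absorption rate 0.5 or 1.0 per hour; within-subject CV 10–30%.

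**1. The plan's own figures.** Fraction of steady state after 72 h = 1 − 2^(−72/t½), at the longest half-life.
- Apixaban: 72/14 = 5.14 half-lives, 97.2% (stated 97%).
- Dabigatran: 72/17 = 4.24 half-lives, 94.7% (stated 94%; exactly 4 half-lives gives 93.75%).

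Both reproduce.

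**2. Dose count.** Text: 6 days × 2 = 12 doses, the last at hour 25 + 11 × 12 = 157. Schedule columns: the last available partner-dose hour is 145, so 11 doses.

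**3. Exact steady state, bolus, no interaction.** Let A be the area over one 12-h interval. Two doses in 24 h give 2A. One dose in 24 h gives A + A × 2^(−12/t½). The ratio is (1 + 2^(−12/t½))/2.
- Apixaban: 0.698 (9 h), 0.776 (14 h).
- Dabigatran: 0.750 (12 h), 0.807 (17 h).

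**4. Superposition of the actual doses, no interaction.** This allows for Day 4 not being fully at steady state, and for absorption. Day 7/Day 4 ratios:

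| Areas compared | Apixaban | Dabigatran |
|---|---|---|
| Same 12 h on both days (AUC0-τ) | 1.01–1.06 | 1.03–1.10 |
| 24 h, two doses on both days (dosing text) | 1.01–1.05 | 1.02–1.08 |
| 24 h, two doses on Day 4, one on Day 7 (schedule columns) | 0.70–0.84 | 0.77–0.90 |

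Steps 3 and 4 together give 0.70–0.84 for apixaban and 0.75–0.90 for dabigatran in the mismatch case.

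**5. Effect on the criteria.** At CV 20%, the within-subject SD on the log scale is √ln(1.04) = 0.198. The standard error of the log ratio is √2 × 0.198/√12 = 0.081. With t(0.95, 11 df) = 1.796, the typical 90% CI is the ratio divided and multiplied by 1.156:
- 1.00: 0.87–1.16
- 0.90: 0.78–1.04
- 0.84: 0.73–0.97
- 0.70: 0.61–0.81

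Simulated chance that the CI lies within 80–125%:

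| Ratio | CV 10% | CV 20% | CV 30% |
|---|---|---|---|
| 1.00 | 99.9% | 65% | 16% |
| 0.81 | 9% | 7% | 4% |
| 0.75 | 0.1% | 0.8% | 1.2% |

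The 50–200% step is passed in about 99% of cases or more at CV 10–20% for ratios down to 0.70. At CV 30% it is passed in 98% at 0.81 and 84% at 0.70.

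**The case against.** The strongest reply is that no mismatch is shown. The partner-drug sampling footnotes are redacted or garbled. In Protocol Tables 2 to 5 the partner-drug sampling row carries one footnote where LT3001 has two, which suggests one sampling schedule for both partner-drug days. The legible part of the SAP's Cohort 4 footnote treats Day 4 and Day 7 alike, and refers to a 24-hour sample taken before the second dabigatran dose. Read literally, that presupposes a second Day 7 dose and puts one dose in each profile. It does not settle the matter, because 24 hours does not fit a second dose due at 12 hours. The reply stands: a reader might infer that the documents prove unequal days, and they do not. They show a conflict about dosing and an unfixed end point.

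The SAP's verb is include, so its list is not strictly closed. AUC0-τ is still calculated and summarised for the partner drugs, and AUC0-t is itself one of the protocol's parameters. So AUC0-τ has not been abandoned; it is missing from the named comparison. Nor does the synopsis commit to AUC0-τ: its steady-state wording is met by any parameter taken on a steady-state day.

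It is also tempting to extend the point to all four cohorts. The dose-count problem cannot arise with once-daily aspirin or clopidogrel. Cohort 2 stays until Day 10 after a Day 9 profile. For Cohort 1, subjects "stay until Day 8, and will have a follow-up visit on Day 15", and Day 8 is the combination day; that raises the possibility of a shorter profile than on Day 5, with no discharge hour or sampling end to confirm it.

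**Conclusion.** The point holds as a gap in specification, with a conditional effect confined to Cohorts 3 and 4. The partner-drug comparison names a parameter without a fixed interval and leaves out one that the protocol lists and the SAP derives.

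There is no artefact if sampling ends at 12 h on both days with quantifiable last samples, or if dosing and sampling match. A false decrease of about 16–30% for apixaban or 10–25% for dabigatran needs all of the following: AUC(0-t) running to 24 h, two doses on Day 4, and one on Day 7. The spread reflects the half-life, accumulation and absorption assumptions. The lower ends should not be read as the expected result.

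In that case the no-effect conclusion at 80–125% would be the casualty; the 50–200% step would rarely be affected unless variability is high. The SAP's partner-drug paragraphs do not restate these bounds, so applying them here rests on Protocol 10.3.2 and on the SAP's reference to a similar model.

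**What to change.** In the four partner-drug paragraphs of SAP 8.3, name AUC0-τ and Cmax as the compared parameters and keep AUC(0-t) as supportive. State τ for each drug, the same on both days: 12 h for apixaban and dabigatran, 24 h for aspirin and clopidogrel. Where the full interval is not sampled on both days, which may apply to Cohort 1, use a partial AUC over the longest interval common to both.

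Reconcile the Day 7 dosing text, the Cohort 3 and 4 schedule columns, and the 24-hour sample footnote in the SAP's Cohort 4 schedule. This review takes no position on which is right.

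The cost is SAP wording, since AUC0-τ is already derived; the partial AUC is a small added derivation. Nothing is lost if the two days turn out to match. The change does not remove the 1.01–1.10 excess that comes from Day 4 not being fully at steady state, which should be noted when the ratios are interpreted.
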